#### 6.6.2.1 Intensive Pharmacokinetic Sampling Schedule

For the intensive PK analysis, blood samples for measurement of defibrotide concentrations will be collected from approximately 25 patients weighing  $\geq 30$  kg who were randomly assigned to receive defibrotide (DP arm), including approximately 10 children ( $\leq 16$  years old) to characterize the PK profile of defibrotide. An attempt will be made to recruit 3 to 5 patients receiving continuous veno-venous hemodialysis (CVVH).

Blood samples (3 mL) will be collected as follows:

- Day +1 post-HSCT and Day +7 post-HSCT at the first defibrotide infusion of the day starting after 6:00 AM at the following time points:
  - Within 15 minutes before the start of the infusion
  - At 2 hours after the start of infusion (within  $\pm 15$  minutes before the end of infusion)
  - At the following times after the start of the infusion: 2.25 hours ( $\pm 5$  minutes), 2.5 hours ( $\pm 10$  minutes), 2.75 hours ( $\pm 10$  minutes), 3.0 hours ( $\pm 10$  minutes), 3.5 hours ( $\pm 15$  minutes), 4.0 hours ( $\pm 15$  minutes), and 5.0 hours ( $\pm 15$  minutes)
- At Day +15 post-HSCT\*, and at Day +30 post-HSCT (for patients still receiving defibrotide):
  - At 2 hours after the start of infusion (within  $\pm 15$  minutes before the end of infusion) at the first defibrotide infusion of the day starting after 6:00 AM

Defibrotide (JZP-381)  
Clinical Trial Protocol: 15-007 Version 4.0

Jazz Pharmaceuticals, Inc.  
20 August 2018

\*NOTE: If hospital discharge occurs prior to Day +15 post-HSCT, the Day +15 post-HSCT PK samples do not need to be collected.

Patients should be carefully monitored so as not to exceed the blood draw maximums detailed in [Appendix 6](#); PK sampling can be eliminated or discontinued if investigator believes such sampling will compromise patient safety by exceeding daily or monthly blood draw maximums or cause need for transfusion (see [Section 7](#) for details).

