16.3 Defibrotide Pharmacokinetic Parameters

Subjects with partial defibrotide concentrations data, protocol violations or events with the potential to affect PK will be evaluated on a case-by-case basis to determine if sufficient data are available for reliable estimation of PK parameters.

PK parameters will be calculated for the patients consented for intensive PK collection on Day +1 and Day +7 post-HSCT; and for patients who developed VOD and received defibrotide for rescue treatment on Day 1 (Protocol Amendment 3) and on Day 14 (Original Protocol, and Protocol Amendments 1&2) after the start of rescue treatment, as data permit.

The defibrotide plasma PK parameters will be calculated using the standard noncompartmental analysis methods according to current working practices and Phoenix WinNonlin (Certara USA, Inc., v6.3 or higher).

All calculations of noncompartmental parameters will be based on actual sampling times for the analysis, but all predose times will be assigned a numerical value of 0 to prevent overestimation of the AUC.

Defibrotide plasma concentrations that are BLQ or missing will be handled the following way:

- Predose samples concentrations that are BLQ or missing will be assigned a numerical value of 0.
- Any other BLQ value will be assigned a value of 0 if they precede quantifiable samples in the initial portion of the profile.
- A BLQ value that occurs between quantifiable data points, especially prior to C_{max} , will be evaluated to determine if an assigned value of 0 makes sense, or if exclusion of the data (flagged in the data and identified to be treated as missing) is warranted.
- Following C_{max} , the BLQ values embedded between 2 quantifiable data points will be treated as missing when calculating PK parameters.
- If a BLQ value occurs at the end of the collection interval (after the last quantifiable activity), it will be set to 0.
- If consecutive BLQ values are followed by quantifiable values in the terminal portion of the concentration curve, these quantifiable values will be excluded from the PK analysis by setting them to missing, unless otherwise warranted by the concentration-time profile.

Where possible the following PK parameters listed in Table 6 will be determined from defibrotide plasma concentrations.

Table 6. PK Parameters to be Summarized

C_{max}	Maximum defibrotide plasma concentration, obtained directly from the observed data

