T_{max}	Time of maximum defibrotide concentration (in hours), obtained directly from the observed data
C_{last}	The last quantifiable defibrotide concentration, obtained directly from observed data
T_{last}	Time of the last quantifiable defibrotide concentration (in hours), obtained directly from the observed data
AUC_{0-t}	Area under the defibrotide concentration-time curve in the sampled matrix from 0 (predose) to time of last quantifiable defibrotide concentration at time “t”
AUC_{tau}	Area under the defibrotide plasma concentration-time curve from 0 (predose) to the end of the dosing period (Day +7 post-HSCT and Days 1 and 14 after the start of rescue treatment in patients from DP arm)
AUC_{0-inf}	Area under the defibrotide plasma concentration-time curve from 0 (predose), extrapolated to infinity by addition of the last quantifiable concentration divided by the elimination rate constant to AUC_{0-t} : $AUC_{0-t} + C_{last} / \lambda_z$ (Day +1 post-HSCT and Day 1 after the start of rescue treatment in patients from BSC arm)
λ_z (k_{el})	Apparent terminal elimination rate constant (in 1/hour), determined by linear regression of the terminal points of the log-linear defibrotide concentration-time curve Visual assessment will be used to identify the terminal linear phase of the defibrotide concentration-time profile. A minimum of 3 data points will be used for the determination.
$t_{1/2}$	Terminal elimination half-life (in hours): $\ln(2) / \lambda_z$
CL	Systemic clearance after intravenous dosing, calculated as 
 • Dose/AUC_{0-inf} (Day +1 post-HSCT and Day 1 after the start of rescue treatment in patients from BSC arm) • Dose/AUC_{tau} (Day +7 post-HSCT and Days 1 and 14 after the start of rescue treatment in patients from DP arm)
V_{ss}	Estimate of the volume of distribution at steady state following intravenous dosing: $MRT_{0-inf} \times CL$, where MRT_{0-inf} is mean residence time extrapolated to infinity

All AUC parameters will be calculated using Linear trapezoidal / Linear Interpolation trapezoidal summation. The minimum requirement for the calculation of AUC will be the

inclusion of at least 3 consecutive plasma concentrations above the lower limit of quantification, with at least 1 of these concentrations following C_{max} .

The PK parameters listed in Table 7 will be calculated for diagnostic or parameter derivation purposes and listed, but will not be summarized.

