Table 7. PK Parameters for Diagnostic or Parameter Derivation Purposes

Span	The time spanned by λ_z (upper λ_z – lower λ_z) divided by the estimated $t_{1/2}$. The $t_{1/2}$ will be estimated over a time period of at least 2 half-lives, where possible. Where a $t_{1/2}$ is estimated over a time period of less than 2 half-lives, it may be flagged in the data listings at the discretion of the Pharmacokineticist, and the robustness of the value will be discussed in the CSR.
$t_{1/2}$, N	Number of data points included in the log-linear regression analysis to determine λ_z A minimum of 3 data points will be used for determination.
Rsqr, adjusted	Goodness of fit statistic for calculation of λ_z A value of ≥ 0.8 for the adjusted R-squared value will be used as the criterion for the reliable estimation of λ_z and reporting of the $t_{1/2}$. If the adjusted R-squared value does not meet this criterion for a given subject the $t_{1/2}$, AUC_{0-inf} , CL, and V_{ss} will be listed but not included in the descriptive statistics.
%AUC _{extr}	Percentage of AUC_{0-inf} obtained by extrapolation: $[(C_{last} / \lambda_z) / AUC_{0-inf} \times 100]$ If %AUC _{extr} is greater than 20% of AUC_{0-inf} , then AUC_{0-inf} , CL, and V_{ss} will be listed but not included in summary statistics.
AUMC _{last}	Area under the first moment curve (AUMC) from 0 (pre-dose) to time of last quantifiable defibrotide concentration at time “t”
AUMC _{0-inf}	Area under the first moment curve (AUMC) extrapolated to infinity, based on the last observed concentration, calculated as $AUMC_{last} + (T_{last} \times C_{last}) / \lambda_z + C_{last} / \lambda_z$
MRT _{0-inf}	Mean residence time extrapolated to infinity, calculated for infusion models as $(AUMC_{0-inf} / AUC_{0-inf} - TI) / 2$, where TI is infusion time

All PK parameters will be summarized by visit and study arm using descriptive statistics as described in Section [16.1](#). Geometric mean will not be calculated for T_{max} and T_{last} .

The following summaries will be provided:

- Defibrotide plasma pharmacokinetic parameters following defibrotide infusion at 6.25 mg/kg on Day +1 post-HSCT

- Defibrotide plasma pharmacokinetic parameters following defibrotide infusion at 6.25 mg/kg on Day +7 post-HSCT
- Defibrotide plasma pharmacokinetic parameters following defibrotide infusion at 6.25 mg/kg after the start of rescue treatment by Visit.

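### SAP Table 7 drops clearance from the PK summaries by AUC0-inf and terminal-slope criteria even where Table 6 computes it from AUCtau, and Table 6 gives BSC-arm rescue Day 14 no clearance rule

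*SAP*

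**What the plan says.** SAP 16.3, Table 6 uses two definitions of CL:

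- Dose/AUCtau for "Day +7 post-HSCT and Days 1 and 14 after the start of rescue treatment in patients from DP arm". AUCtau itself is limited to the same profiles.
- Dose/AUC0-inf for "Day +1 post-HSCT and Day 1 after the start of rescue treatment in patients from BSC arm". AUC0-inf is limited to these.

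Table 7 then sets two filters:

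- A value of at least 0.8 "for the adjusted R-squared value will be used as the criterion for the reliable estimation of" the terminal rate constant. If it is not met, t1/2, AUC0-inf, CL and Vss "will be listed but not included in the descriptive statistics".
- If %AUCextr exceeds 20% of AUC0-inf, then AUC0-inf, CL and Vss "will be listed but not included in summary statistics".

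Neither filter is limited by visit or by the AUC from which CL was calculated.

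On scope, the text before Table 6 plans parameters for patients who "received defibrotide for rescue treatment on Day 1 (Protocol Amendment 3) and on Day 14 (Original Protocol" and Amendments 1 and 2), as data permit. It does not restrict Day 14 to one arm. SAP 16.2 plans rescue concentration summaries and figures for both arms, and 16.3 summarizes the parameters by visit and arm.

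**The concern.** CL = Dose/AUCtau does not use AUC0-inf. A limit on how much of AUC0-inf is extrapolated is therefore the wrong test of whether that clearance is reliable. A programmer following Table 7 literally would drop such values from the summary because of a quantity that they do not contain. The 20% rule also works through half-life, so the dropped profiles would not be a random subset.

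Characterizing the pharmacokinetics is a secondary objective (Protocol 2.2, SAP 4.2.2). The intensive group is only about 25 patients (Protocol 6.6.2.1), so losing a few is visible in the steady-state clearance summary. The BSC-arm Day 14 gap is a second, smaller matter: profiles that the SAP puts in scope have no stated route to a clearance.

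**Working it through.** The documents state no PK estimate on this point, so there is no figure to reproduce.

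**Step 1. Which rule covers which profile (Table 6).**

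| Profile | AUC0-t | AUCtau | AUC0-inf | CL |
|---|---|---|---|---|
| Day +1 post-HSCT | yes | no | yes | Dose/AUC0-inf |
| Day +7 post-HSCT | yes | yes | no | Dose/AUCtau |
| Rescue Day 1, DP arm | yes | yes | no | Dose/AUCtau |
| Rescue Day 1, BSC arm | yes | no | yes | Dose/AUC0-inf |
| Rescue Day 14, DP arm | yes | yes | no | Dose/AUCtau |
| Rescue Day 14, BSC arm | yes | no | no | none |

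Vss is defined as MRT0-inf × CL. The last row therefore has no Vss either, although AUC0-t, Cmax, Tmax, the terminal rate constant and t1/2 still apply to it.

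**Step 2. Where the 20% limit falls.** Inputs: 2-h infusion every 6 h (SAP 4.4) and last sample 5 h after the start of infusion (SAP 16.2). Assumptions: one compartment, steady state, infusion rate/CL scaled to 1, so that AUCtau = 2. With k = ln 2 / t1/2:

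- C(2) = (1 − e^(−2k)) / (1 − e^(−6k)), and C(5) = C(2)·e^(−3k)
- tail to infinity = C(5)/k
- part of AUCtau after the last sample = (C(5)/k)·(1 − e^(−k))
- %AUCextr = tail / (AUC from 0 to 5 h + tail)

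Example, t1/2 = 2 h: k = 0.3466, C(2) = 0.5/0.875 = 0.571, C(5) = 0.202, tail = 0.583. The 5 to 6 h segment is 0.583 × 0.293 = 0.171, which is 0.171/2 = 8.5% of AUCtau. AUC from 0 to 5 h is 2 − 0.171 = 1.829. %AUCextr = 0.583/(1.829 + 0.583) = 24.2%.

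| t1/2 (h) | %AUCextr | share of AUCtau after 5 h |
|---|---|---|
| 0.5 | 0.5% | 0.4% |
| 1 | 6.6% | 3.4% |
| 1.5 | 15.7% | 6.4% |
| 1.75 | 20.1% | 7.6% |
| 2 | 24.2% | 8.5% |
| 3 | 37.5% | 11.0% |

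The crossing is at about 1.75 h at steady state and 1.69 h for a single dose; linear trapezoids at the protocol sampling times give 1.72 h. At that point about 92% of AUCtau is still observed.

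**Step 3. Effect on summarized CL.** Half-life, variability and assay error are not in the documents, so all are assumed: median t1/2 as shown, CV of CL 30 to 50%, CV of volume 0 to 60% independent of CL, residual error 10 to 20%. Both filters were applied to simulated steady-state profiles on the intensive schedule (20,000 per setting).

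| Median t1/2 (h) | Profiles retained | Geometric mean true CL, retained / all |
|---|---|---|
| 0.5 | 95–100% | 1.00–1.03 |
| 1 | 75–96% | 1.03–1.16 |
| 1.5 | 52–68% | 1.09–1.32 |

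These shifts depend on CL and volume being independent. If volume is proportional to CL, every patient has the same half-life, and a filter on half-life does not select on CL at all.

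**The case against.** **The 20% rule may not reach AUCtau visits.** %AUCextr is a percentage of AUC0-inf, and Table 6 reports AUC0-inf only for Day +1 and BSC-arm rescue Day 1. A reader could apply the rule only there. However, Vss needs MRT0-inf, which needs AUC0-inf, at the other visits too. The quantity will therefore exist, and Table 7 names CL without qualification. The ambiguity does not remove the problem.

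**The design suggests a short half-life.** Table 7 wants the terminal slope to span at least 2 half-lives where possible. From the end of infusion to the last sample is 3 h, which implies 3/2 = 1.5 h or less. If half-lives are mostly well below 1.7 h, few profiles are dropped. This stands, and it is why the size is given as a range starting at zero.

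**The fit filter has some basis.** The dosing interval is 6 h and sampling ends at 5 h, so AUCtau may itself need the terminal slope for the last hour. This also stands. Exempting all AUCtau-based CL from any criterion would go too far.

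**The damage is limited.** Excluded values stay in the listings, the output is descriptive, and no hypothesis test depends on it. Protocol 6.6.2.5 and 9.11 also plan population PK estimates of clearance from all samples. SAP 16.1, however, describes that analysis for the sparse-sampling subjects and reports it outside the CSR, so it does not repair the CSR summary.

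Four stronger inferences are tempting and are not supported:

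- *Clearance is overstated.* No half-life, variability or volume is given. Bias is near zero at a median of 0.5 h, and can vanish or reverse if CL and volume rise together, for example with body size. The R-squared filter selects on fit, and on slow elimination only indirectly.
- *BSC-arm Day 14 has no AUC.* AUC0-t has no visit or arm limit.
- *The patients lost are those on CVVH or with renal or multi-organ dysfunction.* The protocol says only that recruitment of 3 to 5 CVVH patients will be attempted; nothing says that such patients clear the drug slowly.
- *The BSC arm supplies two thirds of rescue patients.* 28/(28 + 14) gives that fraction, but these planning rates are for VOD or death, not for rescue.

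**Conclusion.** The point holds as a fault in a stated rule. Table 7 applies an AUC0-inf criterion to clearances that do not use AUC0-inf. With this sampling schedule it can discard steady-state values for which about 92% of AUCtau is observed. The selection is against half-lives above about 1.7 h, given a one-compartment model.

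The effect on summarized CL is conditional: about 0% to +32% for assumed median half-lives of 0.5 to 1.5 h with CL and volume independent, and smaller or absent if they rise together. The documents do not say where in that range the trial lies.

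The BSC-arm Day 14 gap is confirmed for AUCtau, AUC0-inf, CL and hence Vss. On its own it would be a matter of missing detail.

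**What to change.** In Table 7:

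- Limit the %AUCextr exclusion of CL to CL = Dose/AUC0-inf.
- For CL = Dose/AUCtau, exclude only when the extrapolated share of AUCtau (last sample to 6 h) exceeds a stated limit such as 20%. With a quantifiable 5 h sample the share stays below 1 h/6 h = 16.7% in the model above, so a 20% limit would act mainly when late samples are missing or below quantitation. The SAP should choose the limit with that in mind.
- Apply the R-squared filter to that CL only where the terminal slope is needed for the last segment.
- Report the number of profiles excluded from each summary, by visit and arm.

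In Table 6, extend AUCtau and CL = Dose/AUCtau on rescue Day 14 to both arms.

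The cost is a few lines of SAP wording and a change to the summary flag, with no new data. The downside is that some less precise CL values stay in the summary.

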#### 5.2.1 Defibrotide Administration

Defibrotide solution is administered intravenously by study site personnel at a dose of 25 mg/kg/day, divided into 4 equal doses of 6.25 mg/kg/dose given as 2-hour infusions every 6 hours. Each dose (infused over a 2 hour  $\pm$ 15 min infusion period) may be administered within  $\pm$ 1 hour of the scheduled dosing time provided that there is at least a 2-hour window between the end of an infusion and the start of the next infusion. Individual doses of defibrotide are determined for individual patients based on body weight at baseline (i.e., the day before conditioning begins for the DP arm, and on the day that conditioning begins for patients in the BSC arm who develop VOD and subsequently receive defibrotide). For the DP arm, 2-4 doses of defibrotide must be administered within 24 hours prior to conditioning. Each of the 4 divided doses per day will be rounded to the nearest 10 mg for adults ( $>35$  kg) and the nearest 5 mg for children ( $\leq 35$  kg) to facilitate efficient drug administration.

After dilution, with D5W or 0.9% sodium chloride, the final concentration of defibrotide for administration should be in the range of 4 to 20 mg/mL, as appropriate for infusion over 2 hours. Detailed procedures for preparation of study drug will be provided separately.

Defibrotide (JZP-381)  
Clinical Trial Protocol: 15-007 Version 4.0

Jazz Pharmaceuticals, Inc.  
20 August 2018

Defibrotide may be held for surgical procedures or to accommodate other urgent medication delivery without necessitating dose modification. For surgical procedures, it is recommended that defibrotide administration be completed more than 2 hours prior to intervention. Scheduling may also be adjusted to accommodate other medications and interventions, such as dialysis. While the intent is to treat every 6 hours, the schedule may be adjusted without rendering the patient ineligible or causing protocol violation as long as the daily dose does not alter substantially.

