#### 6.6.2.5 Pharmacokinetic Parameters

Depending on the number of samples obtained, the following PK parameters for a given patient may be calculated using noncompartmental methods:

- $C_{max}$ : maximum concentration
- $T_{max}$ : time of maximum concentration
- $T_{1/2}$ : elimination half-life
- $AUC_t$ : area under the plasma concentration-time curve to the last quantifiable concentration
- $AUC_{0-\infty}$ : area under the plasma concentration-time curve extrapolated to infinity
- CL: clearance
- V: volume of distribution

Clearance and volume of distribution will also be estimated by population PK analysis using all PK samples collected during the study

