16.2 Defibrotide Plasma Concentrations

The defibrotide plasma concentrations will be summarized by nominal time point using descriptive statistics as described in [Section 16.1](#). Concentrations that are below the limit of quantitation (BLQ) will be treated as a numeric value of 0, and the associated geometric statistics will be designated and reported as not done.

The following summaries will be provided:

- Summary of defibrotide plasma concentrations in subjects consented for intensive PK collection

- On Day +1 and Day +7 post-HSCT: prior to defibrotide infusion, and 2, 2.25, 2.5, 2.75, 3, 3.5, 4 and 5 hours after start of defibrotide infusion;
- On Day +15 and Day +30 post-HSCT: 2 hours post start of defibrotide infusion;
- Summary of defibrotide plasma concentrations in subjects with sparse PK sampling
 - On Day +7 post-HSCT: 2 hours post start of defibrotide infusion, 2 to 4 hours after the end of defibrotide infusion;
 - On Day +15 and Day +30 post-HSCT: 2 hours post start of defibrotide infusion;
- Summary of defibrotide plasma concentrations in subjects who developed VOD and received defibrotide rescue treatment by treatment arm (BSC or DP)
 - On Day 1 after the start of rescue treatment: prior to defibrotide infusion, and 2, 3, 4 and 5 hours after start of defibrotide infusion (Protocol Amendment 3);
 - On Day 7 after the start of rescue treatment: 2 hours post start of defibrotide infusion (Protocol Amendment 3);
 - On Day 14 after the start of rescue treatment: prior to defibrotide infusion, at 2 hours post start of defibrotide infusion, and at 1, 2 and 3 hours after end of defibrotide infusion (Original Protocol), or prior to defibrotide infusion, and 2, 3, 4 and 5 hours after start of defibrotide infusion (Protocol Amendments 1&2)
 - On Day 30 after the start of rescue treatment: 2 hours post start of defibrotide infusion (Original Protocol, and Protocol Amendments 1&2);

Figures of individual and arithmetic mean defibrotide concentration-time profiles (\pm SD, as appropriate) using nominal time points in patients consented to intensive PK collection on Day +1 and Day +7 post-HSCT and in patients receiving defibrotide rescue treatment on Day 1 and Day 14 after the start of rescue treatment, will be presented on linear and semi-logarithmic scales. For graphing purposes, the BLQ values will be considered as missing and, if applicable, 2 neighboring values will be connected.

The following figures will be provided:

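### SAP Table 7 halves the whole expression in the infusion mean-residence-time formula, so Vss calculated as printed is less than half the standard-formula value

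*SAP*

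**What the plan says.** SAP section 16.3 has two parameter tables. Table 6 lists the parameters to be summarised in the CSR. One of them is Vss, described as "Estimate of the volume of distribution at steady state following intravenous dosing" and defined as MRT0-inf × CL.

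Table 7 holds the supporting parameters, which are "calculated for diagnostic or parameter derivation purposes and listed, but will not be summarized". Its last row defines MRT0-inf: "Mean residence time extrapolated to infinity, calculated for infusion models as" (AUMC0-inf/AUC0-inf - TI)/2, with TI the infusion time. The row above it defines AUMC0-inf: "Area under the first moment curve (AUMC) extrapolated to infinity, based on the last observed concentration, calculated as" AUMClast + (Tlast × Clast)/λz + Clast/λz.

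The same section says that the plasma parameters will be "calculated using the standard noncompartmental analysis methods according to current working practices and Phoenix WinNonlin". Every defibrotide dose is an infusion: protocol section 5.2.1 has the daily dose "divided into 4 equal doses of 6.25 mg/kg/dose given as 2-hour infusions every 6 hours", with ±15 minutes allowed on the infusion time. The MRT row therefore applies to every noncompartmental profile in the study.

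**The concern.** As printed, the bracket closes after TI, so the whole difference is divided by 2. The usual infusion correction divides only TI by 2. Neither document states the formula a second time in a form that would correct it.

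The section is also at odds with itself: it promises standard noncompartmental methods and then prints a formula that is not the standard one. Either Table 7 gets programmed and the reported Vss is wrong, or the software routine is used and the SAP misstates how Vss was obtained. In the second case, anyone who checks Vss against Table 7 will find a mismatch.

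Vss is summarised by visit and arm. The noncompartmental analysis covers about 25 intensive-PK patients weighing at least 30 kg, about 10 of them children (protocol section 6.6.2.1), and rescue patients weighing at least 30 kg (protocol section 6.6.2.3; SAP section 16.1).

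**Working it through.** **Inputs.**
- Printed MRT formula and AUMC0-inf formula: SAP Table 7.
- Vss = MRT0-inf × CL: SAP Table 6.
- TI = 2 h (1.75 to 2.25 h with the tolerance) and a 6-hour dosing interval: protocol section 5.2.1.
- Intensive sampling times, SAP section 16.2: "prior to defibrotide infusion, and 2, 2.25, 2.5, 2.75, 3, 3.5, 4 and 5 hours after start of defibrotide infusion". Rescue times under Protocol Amendment 3, same section: 0, 2, 3, 4 and 5 h.
- Linear trapezoids: SAP section 16.3.
- Half-life: not given in either document. The values 0.5, 1 and 1.5 h below are assumptions for illustration.

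The plan gives no numerical MRT or Vss, so there is no figure of its own to reproduce.

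**Algebra, which needs no half-life.** Let r = AUMC0-inf/AUC0-inf. Under a constant-rate infusion the mean input time is TI/2, so r = MRT + TI/2.

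- Standard: r - TI/2.
- Printed: (r - TI)/2 = standard/2 - TI/4.
- Ratio printed/standard = 1/2 - TI/(4 × standard MRT), below 1/2 for any positive TI and MRT.

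At TI = 2 h the loss is half the standard MRT plus 0.5 h. Over TI = 1.75 to 2.25 h, TI/4 runs from 0.44 to 0.56 h. CL is the same in both versions, so Vss has the same ratio. The printed value is negative whenever the standard MRT is below TI/2 = 1 h.

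**Check on cases with a known answer (exact integration, single 2-hour infusion).**
- One compartment, half-life 1 h: k = ln 2/1 = 0.693 per hour, so true MRT = 1/k = 1.443 h and r = 1.443 + 1 = 2.443 h. Standard: 2.443 - 1 = 1.443 h. Printed: (2.443 - 2)/2 = 0.221 h, a ratio of 0.153.
- One compartment, half-life 0.5 h: r = 1.721 h. Printed: (1.721 - 2)/2 = -0.14 h, which is impossible for a residence time.
- Two compartments, true Vss 1.625: standard returns 1.625, printed 0.2125 (ratio 0.13).

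**Illustration on the planned intensive times** (one compartment, steady state at 6-hourly dosing, linear trapezoids, squared λz in the AUMC tail):

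| Assumed half-life (h) | r (h) | Standard, r - 1 (h) | Printed, (r - 2)/2 (h) | Printed below standard | AUC extrapolated |
|---|---|---|---|---|---|
| 0.5 | 2.294 | 1.29 | 0.15 | 89% | 0.6% |
| 1 | 2.772 | 1.77 | 0.39 | 78% | 7.2% |
| 1.5 | 3.306 | 2.31 | 0.65 | 72% | 16.2% |

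On the five rescue times at steady state, r = 2.236, 2.729 and 3.277 h, which gives shortfalls of 90%, 79% and 72%.

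Table 7 drops Vss from the summaries when more than 20% of AUC is extrapolated. In this model that happens near a half-life of 1.72 h, so the Vss values that stay in would be about 70% low or worse.

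**Adjacent row.** The tail of AUMC beyond Tlast integrates to Tlast × Clast/λz + Clast/λz². The printed last term, Clast/λz, has the wrong dimensions. If the exponent really is missing from the source, correcting the bracket alone would leave the steady-state MRT on the intensive times 2% below the fully standard formula at a 1 h half-life and 8% below at 1.5 h.

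**The case against.** Four points can be made on the other side.

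**It may be a defect of text only.** The section names Phoenix WinNonlin and standard methods, and nothing says Table 7 is programmed by hand. If the software's infusion routine supplies MRT, no reported number changes. This stands: the documents do not show which route is taken, and the shortfalls above apply only if the printed formula is used. The cell still needs correcting, because the SAP would otherwise describe a calculation that was not done.

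**The text was read from a PDF.** A moved bracket cannot be fully excluded, and the missing exponent in the row above could be a lost superscript. This also stands, and is why the source page comes first in the fix. The brackets as read are a balanced pair around the difference, so a single dropped character does not explain them.

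**The comparator is not the truth.** In the model the true MRT is 0.72, 1.44 and 2.16 h. With no sample between 0 and 2 h, the standard formula on the intensive times returns 1.29, 1.77 and 2.31 h, which is 79%, 23% and 7% too high. Against the true values the printed formula is 80%, 73% and 70% low. This is correct: fixing the cell does not make Vss accurate at short half-lives. It does not rescue the printed formula.

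**The consequence is small.** Vss is descriptive and reported as data permit. Protocol section 6.6.2.5 gives volume by a second route: "Clearance and volume of distribution will also be estimated by population PK analysis using all PK samples collected during the study". No hypothesis test, efficacy result or safety result uses Vss. All of this is true, and it limits the weight of the point.

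**Conclusion.** The concern holds. The MRT0-inf formula in SAP Table 7 is wrong as written. If it is applied, MRT and Vss are more than 50% below the standard formula on the same data. That bound follows from the algebra and rests on no assumed half-life. The figures of 72% to 89% on the intensive schedule do rest on assumptions: one compartment, a half-life of 0.5 to 1.5 h, nominal sampling times and steady state.

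Whether any reported Vss is affected depends on whether Table 7 or the software routine is used, which the documents leave open. The effect stops at MRT and the descriptive Vss summaries. CL, AUC, half-life, Cmax and the population PK volume do not use this formula, and no efficacy or safety conclusion depends on it. It should be corrected, but it does not threaten the trial's conclusions.

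**What to change.** 1. Check both Table 7 cells against the SAP source page.
2. Change the MRT0-inf cell to AUMC0-inf/AUC0-inf - TI/2.
3. Confirm that the last term of AUMC0-inf is Clast/λz², and correct it if it is not.
4. Confirm that the Vss programming, or the WinNonlin output used for Vss, matches the corrected cell.
5. Add a note that the formula is exact for a single infusion and approximate when drug remains from earlier doses. Under exact integration the carry-over error is -f × TI/2, with f the share of AUC0-inf that comes from earlier doses (0.1%, 3.3% and 9.9% in the illustration). MRT is then 0.2%, 2.3% and 4.6% low at half-lives of 0.5, 1 and 1.5 h.

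The cost is one cell corrected, one adjacent cell checked, a short note and one programming confirmation. Data collection and all other parameters stay as they are.
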